1.3 Calcitriol and Bone Health

Calcitriol could prove to be a safe, low-cost treatment for preserving bone health in breast cancer patients. Human beings obtain Vitamin D from sunlight, food, and supplementation.²⁶ Vitamin D plays a vital role in maintaining proper bone health and works in conjunction with calcium. Higher levels of vitamin D have been shown to increase the intestinal absorption of calcium.²⁷ One study demonstrated that an increase in serum vitamin D produced a 45%-65% increase in intestinal absorption of calcium.²⁸ Although no consensus exists on optimal vitamin D levels, most experts agree a 25-hydroxyvitamin D level of less than 20 ng per milliliter is deficient.²⁹ Based on this level, it is estimated more than 1 billion people worldwide and between 40%-100% of elderly U.S. residents are vitamin D deficient.³⁰⁻³³ More than 50% of postmenopausal women already under treatment for osteoporosis have deficient vitamin D levels.^{34, 35}

Bone health is a major concern in women undergoing treatment and who have completed treatment for breast cancer. Cancer-treatment-induced bone loss (CTIBL) is a long-term side-effect of various breast cancer treatments.³⁶ Chemotherapy, hormone therapy, and irradiation frequently lead, either directly or indirectly, to bone mass depletion in breast cancer patients.³⁷ Studies have documented accelerated bone loss in breast cancer patients, and this bone loss frequently goes undiagnosed.³⁸⁻⁴⁰ Breast cancer survivors have greater bone loss than women of similar age who were not diagnosed with cancer.⁴¹⁻⁴³ Risk factors for bone loss are already present in many women prior to a breast cancer diagnosis.⁴⁴ Treating bone loss in a prophylactic manner leads to greater success than delayed treatment.^{45, 46} The Women's Health Initiative (WHI) and other

studies have found that postmenopausal breast cancer survivors had increased risk of fractures.⁴⁷⁻⁴⁹

[figure not shown]

Fig. 2. Extent of bone loss due to cancer therapy. Menopausal women lose bone at a rate of 1% to 2% yearly. Cancer treatments, such as aromatase inhibitor therapy and chemotherapy, accelerate this process, leading to significant bone loss and subsequent skeletal complications (39, 75-79). Adapted from Skeletal Complications Across the Cancer Continuum CME Lecture 2005 series with permission from the Postgraduate Institute for Medicine.

The American Society of Clinical Oncology (ASCO), however, recommends pharmaceutical interventions (bisphosphonates) only after a severe amount of bone loss in patients considered osteoporotic.⁵⁰ Bisphosphonates produce a host of side effects, including poor GI absorption, nausea, and diarrhea for the oral medications.⁵¹ Fever, flu-like symptoms, and myalgia are seen in treatment with iv bisphosphonates.⁵² Among the most serious side-effects is osteonecrosis of the jaw, which can require surgical intervention.^{53, 54} All of these side-effects lead to poor compliance. Studies have shown that compliance with bisphosphonate therapy is low, with 57% of patients considered non-compliant after 2 years.⁵⁵

[figure not shown]
While bone loss is a significant problem for breast cancer patients and pharmaceutical interventions result in less than ideal compliance, vitamin D and calcitriol supplementation could be an effective intervention for bone health. A review of clinical trials found vitamin D supplementation had a positive effect on bone mineral density.⁵⁶ Trials that used a low-dose vitamin D intervention (≤ 400 IU/d) failed to significantly reduce bone fractures.^{57, 58} In contrast, interventions that used a higher dose of vitamin D (≥ 700 IU/d) produced significant positive effects on fracture prevention.⁵⁹⁻⁶³ A pooled analysis of those trials found vitamin D significantly reduced the risk of hip fracture by 26% and any nonvertebral fracture by 23%.⁶⁴ Other interventions used the active vitamin D analog, calcitriol, because of its higher efficiency and quicker absorption. These trials demonstrated calcitriol is effective in maintaining bone mineral density and reducing fractures.⁶⁵⁻⁷¹ A pooled analysis revealed calcitriol interventions significantly reduced the rate for nonvertebral fractures by 48% and all fractures by 48%. A comparative analysis found that calcitriol was significantly more effective at reducing bone loss and fractures than native vitamin D.⁷² A pooled analysis also concluded that vitamin D analogs (calcitriol) were more effective in preserving BMD than placebo, no treatment, plain vitamin D₃ and/or calcium

alone.⁷³

In addition to regulating bone health, vitamin D also protects against falls and helps maintain muscular strength.^{74, 75} A meta-analysis of 5 randomized clinical trials reported a 22% reduction in falls in those receiving vitamin D supplementation.⁷⁶ Similarly, calcitriol protects against falls. One trial found those supplemented with calcitriol, in addition to having adequate calcium intake, had a 55% reduction in falls.⁷⁷ A 2001 intervention trial reported a significant reduction in the number of falls for those treated with calcitriol compared to placebo.⁷⁸ A recent comparative meta-analysis concluded that calcitriol was more effective at preventing falls than native vitamin D.⁷⁹

1.4 Calcitriol Dosing

To date, the maximum tolerated dosage of vitamin D has not been clearly established. Many clinical trials have failed to produce protective bone health effects from vitamin D because the supplementation level was too low.^{80, 81} Some researchers have suggested that interventions should use high, intermittent doses of vitamin D to increase serum levels and overcome low adherence.⁸² Trials that supplemented with ≥ 700 IU/d of vitamin D were able to show protection against bone loss.⁸³⁻⁸⁷ In both North America and Europe, the upper limit for vitamin D intake is considered to be 2,000 IU/d.^{88, 89} However, many researchers, even government committees, believe numerous individuals are vitamin D deficient and this upper limit is too low.⁹⁰⁻⁹² These recommendations were formulated out of concern for safety and to prevent toxicity such as hypercalcemia.⁹³ However, many clinical trials have administered vitamin D doses well above the upper limit. One trial administered 100,000 IU of vitamin D every four months for five years without reports of toxicity.⁹⁴ Another intervention administered 50,000 IU/d of vitamin D for a period of 8 weeks without a change in serum calcium.⁹⁵ A long-term trial was able to administer 18,000 IU/d (9 times higher than the upper limit) of vitamin D for a period of 5 years without evidence of adverse events.⁹⁶ A review of these trials shows that vitamin D is not toxic at intakes much greater than previously considered unsafe.⁹⁷

[figure not shown]

Fig. 1 Hip fracture efficacy by total estimated vitamin D intake (all trials used oral cholecalciferol) considering adherence to treatment. Compliance in the different trials was reported as follows: Lips (400 IU per day)=85% [36], Record (800 IU per day)=47% [13], WHI* intent-to-treat analysis (400 IU per day plus additional reported mean vitamin D intake of 360 IU)=59% [14], Trivedi (100,000 IU every 4 months equals 820 IU per day)=76% (& includes hip plus forearm fractures) [38], Chapuy (800 IU per day)=84% [57], WHI**-compliant women

(400 IU per day plus additional reported mean vitamin D intake of 360 IU)=100% [14]. In most studies, being compliant was defined as taking 80% or more of the study medication. The x-axis gives the DiaSorin equivalent 25(OH)D levels in nmol/l achieved in the treatment arm of the trials. #For the Record trial a HPLC method has been used for 25(OH)D measurement with an unknown DiaSorin equivalent value. In the WHI trial, 25(OH)D levels have not been measured at follow-up in the study population (n.a. = not available) 98

The pattern is similar in terms of dosing for calcitriol. Higher doses of calcitriol were typically not possible when given on a daily dosing schedule because of the development of hypercalcemia and hypercalcuria.^{99, 100} In recent years, researchers discovered that a less frequent dosing schedule allowed them to circumvent dose-limiting toxicities.^{101, 102} A weekly administration of high-dose oral calcitriol was shown to be safe in cancer patients.^{103, 104} The dosage was not limited by toxicities, but rather by nonlinear pharmacokinetics.¹⁰⁵ Subsequent studies have shown substantial dose escalation was possible when calcitriol was administered once a week.¹⁰⁶⁻¹¹³ Trump et al. were able to administer 12 µg of calcitriol daily for three consecutive days (36 µg/week) without any dose-limiting toxicities.¹¹⁴ A trial of prostate cancer patients found that 60 µg/week of calcitriol was well tolerated.¹¹⁵ Recently, 7 separate clinical trials were able to administer 45 µg/week (or 0.5 µg/kg/week) of calcitriol to patients undergoing adjuvant cancer therapy.¹¹⁶⁻¹²² In the larger trials, participants remained on calcitriol for one year or longer.^{123, 124} These studies demonstrated that this dose was well tolerated, and adverse events were extremely rare. In fact, a number of studies have demonstrated the safety of doses much greater than 45 µg/week. A phase I study in patients with cancer found calcitriol was well tolerated at a dose of 165 µg/week.¹²⁵ Another phase I trial administered calcitriol at doses up to 38 µg/d

for three consecutive days (114 µg/week) without dose-limiting toxicity.¹²⁶ These trials established intermittent oral dosing of calcitriol as a method of significant dose escalation and produced potentially therapeutic levels.¹²⁷ Additionally, calcitriol enhances the effects of radiation, chemotherapy, hormone therapy, and other antineoplastic treatments.¹²⁸⁻¹³¹ Based on previous trials, the 45 µg/week of calcitriol is an ideal dose to elicit positive effects and should pose only a minimal risk to the subject enrolled in this study. Nonetheless, potential toxicities related to calcitriol will be closely monitored.

1.5 Exercise and Bone Health

Exercise and physical activity, in general, have beneficial effects on bone health. Several clinical trials demonstrate that various exercise interventions have positive effects on bone mineral density.¹³²⁻¹³⁸ These trials found that exercise was beneficial in postmenopausal women, who are those at the highest risk for osteoporosis. A pooled analysis found a mean difference of 1.79 (p<0.01) in spinal bone mass density when an exercise intervention was compared to controls.¹³⁹ In terms of specific exercises, walking interventions are effective in preventing bone loss.¹⁴⁰⁻¹⁴² Interventions examining the effect of exercise on bone health in breast cancer patients have been limited. Nevertheless, exercise interventions in breast cancer patients are also protective against bone loss.^{143, 144} One single-arm clinical trial in breast cancer patients found a combination exercise and vitamin D had significant effects on bone health.¹⁴⁵ In addition to the benefits of aerobic exercise on bone health, resistance training has also been shown to be effective.¹⁴⁶⁻¹⁴⁹ A pooled analysis revealed a weighted mean difference of 2.50 (p=0.02) in spinal bone density when resistance training was compared to placebo.¹³⁹ The literature shows that improvements in bone mineral density for resistance training were greater with a higher resistance/lower repetition regimen in older populations.¹⁵⁰⁻¹⁵² Therefore, it is recommended that women at higher risk for osteoporosis (e.g. breast cancer patients) train with higher resistance and fewer repetitions, which is the regimen that this protocol will follow.¹⁵³

1.6 Summary

We propose to conduct a feasibility and efficacy pilot in breast cancer patients studied over 12 weeks to identify the ability to participate in a high-dose oral calcitriol and exercise intervention and to investigate the subsequent effects on bone health. The study will accrue 54 patients and is intended to provide pilot data for a later grant submission. The anticipated results could provide important information with clinical and methodological applications. Acquiring a better understanding of treatments capable of preserving bone health in breast cancer patients could lead to a higher quality of life and functional independence for these survivors.

2.0 Objectives

Both the calcitriol and exercise arms are aimed at reducing fracture risk by maintaining proper bone density, thereby preventing osteoporotic/osteopenic conditions and increasing muscle mass. Both calcitriol and exercise are efficacious in maintaining proper bone health and muscle mass among the general population, but little research has been done on breast cancer patients and survivors. The combination of calcitriol and exercise, which function through different but similar mechanisms, could produce interactive effects in reducing fracture risk among breast cancer survivors.

Hypothesis: A combination of calcitriol 45 µg/week along with a structured home-based walking and progressive resistance exercise program will be efficacious in preventing bone resorption, as defined by NTx level, and in increasing bone formation, as defined by BAP level, among survivors of invasive breast cancer.

2.1 Primary Objective

2.1.1 To collect data on the efficacy and feasibility of a 12-week supplementation of calcitriol 45 µg with/without an accompanying structured home-based walking/progressive resistance exercise program for improving bone health among breast cancer survivors.

2.2 Secondary Objectives

2.2.1 To collect data on the efficacy and feasibility of a 12-week supplementation of calcitriol 45 µg with/without an accompanying structured home-based walking/progressive resistance exercise program for increasing **strength** among breast cancer survivors.

2.2.2 To collect data on the efficacy and feasibility of a 12-week supplementation of calcitriol 45 µg with/without an accompanying structured home-based walking/progressive resistance exercise program for improving **skeletal muscle mass** among breast cancer survivors.

3.0 Subject Eligibility

Inclusion Criteria:

3.1 Must be female.

3.2 Women of child-bearing potential (i.e. women who are pre-menopausal or not

surgically sterile) must use acceptable contraceptive methods (abstinence, intrauterine device (IUD), or double barrier device) and must have a negative serum or urine pregnancy test within 1 week prior to beginning treatment on this trial. Contraceptive use needs to be continued at least 1 month after the trial has ended.

- 3.3 Must provide informed consent.
- 3.4 Must be willing to discontinue use of calcium and/or vitamin D supplements.
- 3.5 Participants must have an ionized serum calcium level within normal limits (1.19-1.29mmol/L) and a total corrected serum calcium of < 10.2mg/dl.
- 3.6 Must have a functional capacity rating of ≤ 2 on the Eastern Cooperative Oncology Group (ECOG) performance status when assessed at baseline.¹⁵⁴
- 3.7 Must have the approval of their treating physician (or physician's nurse practitioner or physician's assistant) to participate in sub-maximal physiological fitness testing and a low to moderate home-based walking and progressive resistance exercise program and to receive the 12-week supplementation of calcitriol 45 μ g. Participants assigned to either of the calcitriol treatment arms will be instructed to stop taking calcium and/or vitamin D supplements.
- 3.8 Must be less than five years from the diagnosis of breast cancer and have received chemotherapy, radiation therapy, and/or hormonal therapy. Chemotherapy and radiation therapy, if received, must have been completed prior to study enrollment. Hormonal therapy may be ongoing.

Exclusion Criteria:

- 3.9 Subjects with life-threatening conditions that would preclude them from breast cancer treatment including chronic cardiac failure, which is unstable despite medication use, uncontrolled hypertension, uncontrolled diabetes mellitus, or unstable coronary artery disease.
- 3.10 Patients who had a myocardial infarction within the past year.
- 3.11 Patients with severe metabolic disorders, which includes phenylketonuria (PKU), homocystinuria, and Fabry's disease, that would preclude them from taking calcitriol.
- 3.12 Patients with impaired renal function (CRCL < 60 mL/min) or who had kidney stones (calcium salt) within the past 5 years.
- 3.13 Patients with hypercalcemia (corrected serum Ca > 10.2 mg/dl) or a history of

hypercalcemia or vitamin D toxicity.

- 3.14 Patients currently taking calcium supplements or aluminum-based antacids must be willing to discontinue their use if they are to enroll in the study.
- 3.15 Patients currently taking vitamin D supplements must immediately discontinue their use if they are to enroll in the study.
- 3.16 Patients with a known sensitivity to calcitriol.
- 3.17 Women who are pregnant or lactating.
- 3.18 [REDACTED]
- 3.19 [REDACTED]
- 3.20 Patients not capable of participating in an exercise intervention due to severe knee arthrosis or ligament/cartilage injuries of the lower extremities.
- 3.21 Women currently using oral contraception.
- 3.22 Women with malabsorptive syndromes (i.e. cystic fibrosis, chronic pancreatitis) or taking medications that decrease the absorption of fat soluble vitamins (i.e. Orlistat, Questran).

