5.4 Physiological and Psychological Assessments

- 5.4.1 Blood sampling at four time points (baseline, day 5, week 6, and week 12) will be done to estimate bone resorption and formation and as a safety check for hypercalcemia. Measures of bone pathology will be performed through the Associated Regional and University Pathologists (ARUP) Laboratories. Pre and post-intervention tests for Cross-linked N-teleopeptide of type I collagen (NTx), a specific indicator of bone resorption will be performed. In addition, pre and post-intervention tests for bone-specific alkaline phosphatase (BAP), an indication of bone formation, will be performed.
- 5.4.2 The blood draws for estimation of NTx and BAP will use 2 red top tubes for serum.
- 5.4.3 All blood draws will occur in the General Clinical Research Center (GCRC) and the blood will be drawn by research personnel in the GCRC. The time of day will be noted, with future assessments at approximately the same time of day during post-testing and follow-up.
- 5.4.4 All patients will be given a measure of physical activity (Aerobics Center Longitudinal Physical Activity Questionnaire (ACLS)), fatigue

(Functional Assessment of Chronic Illness Therapy Fatigue Subscale (FACIT-F); Brief Fatigue Inventory (BFI); Multidimensional Fatigue Symptom Inventory (MFSI)), QOL (Functional Assessment of Chronic Illness Therapy with Fatigue (FACIT-F)), to complete at home at the appropriate times (i.e. during baseline and post-testing). (Note: Pilot use of the questionnaire packet indicates an average completion time of ≤ 30 minutes).

[figure not shown]
5.4.5 All patients will be evaluated on aerobic capacity (VO₂max Treadmill Test), muscular strength (handgrip dynamometry, 7-10 repetition maximum test), gait (tandem walk test), and skeletal muscle mass (bioelectrical impedance). All physiological fitness testing will be administered according to the Guidelines for Exercise Testing and Prescription (GETP) as outlined by the American College of Sports Medicine (ACSM).

5.5 Calcitriol 45 μ g Arms 1 & 3

5.5.1 The calcitriol 45 μ g arms 1 & 3 will follow the guidelines listed below:

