5.7 Commencement of a low to moderate walking and progressive resistance exercise program is not associated with any severe side effects and risks are minimal for individuals with no cardiopulmonary, orthopedic, or age-identified high risk factors as determined by the patient's treating physician (or designee). The chance of a cardiac event is rare once coronary disease has been excluded with reasonable certainty. Approximately 1 death per 15,000-20,000 healthy men per year occurs during jogging; this risk is much lower in women. A transient increase in blood pressure may occur with all types of exercise. Although unlikely, the risks involved in a low to moderate walking and progressive resistance exercise program are musculoskeletal—possibly mild muscle soreness, a muscle strain, or related injuries such as tripping. Overall, the risk level for participation in a low to moderate Home-Based Walking and Progressive Resistance program is minimal. Risks associated with a 6-minute walk test are similar to participation in a low to moderate walking exercise program and are minimal for individuals with no cardiopulmonary, orthopedic, or age-identified high risk factors as determined by the patient's doctor. 7-10 Repetition maximum tests for strength may cause minor stiffness and/or tenderness in muscles for a few days following testing. The nature of these assessments will require a level of exertion causing temporary changes such as an increase in heart rate and blood pressure, both of which are normal responses to moderate exercise. There is a small risk of irritation to the skin from the electrodes used for the BIA analysis. Lying under the canopy for resting metabolic testing creates a risk for some subjects to feel anxious or claustrophobic. Every effort will be made to minimize the risks for all study procedures through the approval of the treating physician to enter the study, supervision of all testing and exercise prescription by an American College of Sports Medicine certified Health and Fitness Instructor or a physician (or physician's designee) when necessary according to American College of Sports Medicine Guidelines, the use of standardized guidelines for exercise testing and prescription provided by the American College of Sports Medicine and resting metabolic rate testing and bioelectrical impedance analysis. Regarding the risks for resting metabolic testing, if patients feel claustrophobic during the resting metabolic test it will be stopped. Electrodes will be removed

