6.1.2.2 The **Pedometer** device will be used to assess duration of physical activity via steps walked during the time out of bed. [Note: Participants NOT assigned to the exercise arm will give back their pedometer after the 5-day baseline measure and will have the pedometer reissued for the 5-day measure at the end of the trial.]

6.1.2.3 The **Daily Journal** is designed to track daily physical activity. The participant will be asked to complete the journal each night immediately prior to sleeping and record steps and miles walked, caloric expenditure, and a Rating of Perceived Exertion.

6.1.3 Aerobic capacity will be assessed using a **VO2max Treadmill Test** as a measure of compliance using a modified “Branching Treadmill Protocol”. Participants begin at a normal walking speed (2.5 mph) and 0% grade.

After 2 min. the speed is increased to a faster walking speed (3.0 mph) and 0% grade. After 2 min, the speed is increased to 3.5 mph and 2% grade. Thereafter, only the grade is increased by 2% every 2 min. Oxygen consumption (VO₂), carbon dioxide production (VCO₂), and flow rate will be measured continuously. The test is ended when the participant wants to stop. An MD is available onsite in the hospital during all tests as outlined by the ACSM fitness testing guidelines. In preparation for the exercise treadmill test, subjects will be instructed to fast for 4 hrs prior to the test and they will be asked to rest quietly on a bed in a quiet room for 30 minutes under a clear canopy which is placed over their head. During this 30 minute period, they will have their resting metabolic rate measured for 30 minutes using continuous, computerized open-circuit indirect calorimetry (Sensormedics® Vmax). A 6-Minute walking test may be substituted for the treadmill test in the event the person is not able to complete it. This is a sub maximal measurement using a 6 minute walk protocol. Participants are given a short warm up and cool down walking protocol in the test walking area in the University of Rochester. Participants walk for a total of 6 minutes and cover as much distance as they can during this time. Upon completion of the test, the total distance walked is used to calculate an estimate of aerobic capacity (VO_{2max}:Maximal Oxygen Consumption).

6.1.4 **Muscular fitness** will be assessed using two measures: a handgrip dynamometer test and a 7-10 repetition maximum strength test.

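### Inclusion 3.7 words the physician's approval as covering sub-maximal fitness testing, but the planned aerobic test is a VO2max treadmill test with no written effort ceiling, which the risk text in 5.7 does not name

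*Combined protocol and SAP*

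**What the plan says.** **The approval.** Criterion 3.7 asks for approval from the treating physician (or that physician's nurse practitioner or assistant) for three things: to "participate in sub-maximal physiological fitness testing", to follow the home exercise program, and to receive calcitriol.

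**The tests.** Section 5.4.5 opens with "All patients will be evaluated on aerobic capacity" and gives the VO2max treadmill test as the measure. The same list includes handgrip, the 7-10 repetition maximum, the tandem walk and bioelectrical impedance. It continues: "All physiological fitness testing will be administered according to the Guidelines for Exercise Testing and Prescription". Section 5.3.1 puts the treadmill test in the baseline battery, and the table in 8.0 schedules it at time 0 and 12 weeks. Section 7.1.2 lists it as the secondary measure of aerobic capacity.

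**The treadmill procedure.** Under 6.1.3 the woman starts at 2.5 mph and 0% grade and moves to 3.5 mph and 2% grade. "Thereafter, only the grade is increased by 2% every 2 min". The test stops when she decides to stop.

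**The fallback.** Also in 6.1.3: "A 6-Minute walking test may be substituted for the treadmill test in the event the person is not able to complete it". The next sentence says of the substitute: "This is a sub maximal measurement using a 6 minute walk protocol".

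**The risk text.** Section 5.7 states: "Risks associated with a 6-minute walk test are similar to participation in a low to moderate walking exercise program". It also describes risks of the 7-10 repetition maximum, bioelectrical impedance and resting metabolic tests. The treadmill test is not named. The section then says: "Every effort will be made to minimize the risks for all study procedures through the approval of the treating physician to enter the study", and goes on to list supervision and standard guidelines as further measures.

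**The concern.** Criterion 3.7 is the most specific visible statement of what the treating physician approves, and it describes the fitness testing as sub-maximal. The aerobic test that the protocol plans is not described that way anywhere. A physician who knew the study only from 3.7 and 5.7 would expect something like a 6-minute walk.

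The stake is patient safety, not inference. Section 5.7 puts physician approval first among its risk-reducing measures and makes its statement of minimal risk depend on the treating physician's assessment of cardiopulmonary, orthopedic and age-related risk. The visible exclusions remove unstable coronary disease (3.9) and infarction within the past year (3.10), but not stable coronary disease. Criterion 3.6 admits women with ECOG status up to 2. The physician's assessment is therefore an important individual screen, and it should be made for the test the woman will take. Under 4.1 baseline assessments are completed before randomization, so the mismatch concerns women in all four arms.

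**Working it through.** There is no figure to reproduce. The check sets the sections side by side.

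1. **Do 3.7 and 5.4.5 refer to the same thing?** Both use the term physiological fitness testing. In 3.7 it is qualified as sub-maximal. In 5.4.5 it is unqualified and follows a list that begins with the VO2max treadmill test. The natural reading is that 3.7 is meant to cover that battery.

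2. **Is the treadmill test sub-maximal as written?** Section 6.1.3 gives no heart-rate, workload or time limit. The grade goes up every 2 minutes and the only written end point is the woman's wish to stop. A woman may stop early, so some tests will be sub-maximal in practice, but a self-chosen stop does not cap effort.

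3. **How does 6.1.3 use the term?** It applies sub-maximal to the 6-minute walk and not to the treadmill test in the same paragraph.

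4. **Who takes which test?** The treadmill test is the default for all patients at two time points. The walk replaces it only when a woman cannot complete the treadmill test. No route to the walk exists for a woman whose physician approves sub-maximal testing and nothing more.

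5. **Does 5.7 cover the treadmill test?** It names the 6-minute walk, the 7-10 repetition maximum, bioelectrical impedance and resting metabolic rate, and likens the exertion to moderate exercise. The only aerobic test it names is the substitute.

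6. **Does another section widen the approval?** Section 4.1 mentions physician consent, 5.3.1 treats physician approval as one of the eligibility criteria, and 5.7 speaks of approval to enter the study. None lists the tests covered.

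Two groups of sections result. Sections 3.7 and 5.7 fit a study with a walk test. Sections 5.3.1, 5.4.5, 6.1.3, 7.1.2 and the table in 8.0 describe a study with a treadmill test.

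**The case against.** The strongest reply is that VO2max is only a label. The procedure starts at a walking pace, the woman decides when to stop, and no plateau or heart-rate criterion of maximal effort is written. This stands in part. A reader might infer that every woman undergoes a maximal test, and the documents do not support that: maximal effort is not demanded, and the walk may be substituted. What remains is that nothing makes the treadmill test sub-maximal either.

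A second reply is that approval is not confined to 3.7. Section 4.1 lists physician consent alongside meeting the eligibility criteria, and 5.7 refers to approval to enter the study as protection for all procedures. This also stands in part. A reader might infer that physicians approve sub-maximal testing and nothing else, so that women are tested outside their approval. The text does not go that far: 3.7 contains no word such as only, and the broader phrases could reflect a fuller approval. They do not say which tests that approval includes, so they leave the mismatch in place.

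Third, other safeguards exist: a physician on site during treadmill testing and the ACSM guidelines (6.1.3), certified supervision and General Clinical Research Center procedures (5.7), and the cardiac exclusions. The guidelines or center procedures may contain stopping limits. These reduce the risk of the test but do not change what 3.7 describes.

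A reader might also extend the point to handgrip, because 6.1.4.1 describes a maximal contraction. A brief grip effort is not a meaningful safety conflict, and the term sub-maximal in 6.1.3 concerns an aerobic test. The point rests on the treadmill test alone.

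**Conclusion.** The inconsistency is real and minor. As worded, the approval in 3.7 and the testing risks in 5.7 do not match the planned aerobic test. It bears on the default test for all patients, in every arm and at both scheduled visits. The documents give no numerical measure of its effect: a count of scheduled treadmill tests would describe exposure, not women wrongly approved or harmed.

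No harm is shown, and none should be inferred. What physicians actually sign is unknown. The approval form and consent pages are not available and criteria 3.18 and 3.19 are redacted, so any of these may already deal with the treadmill test. The conclusion assumes only that 3.7 and 5.7 mean what they say. The NTx and BAP analyses are unaffected. Aerobic capacity is a secondary measure (7.1.2), which 6.1.3 says is used to gauge compliance.

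The correction is worth making before the first baseline test, because it aligns a safeguard that 5.7 relies on and costs almost nothing.

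**What to change.** Either of two routes resolves it.

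**Match the approval to the test.**
- In 3.7, replace the sub-maximal wording with the named tests: the VO2max treadmill test (or 6-minute walk) and the 7-10 repetition maximum test. Align the approval form if it does not already name them.
- In 5.7, add the treadmill test and its risks.
- In 6.1.3, extend the substitution sentence so that a woman whose physician approves only sub-maximal testing takes the 6-minute walk.

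**Match the test to the approval.** Keep 3.7 and write a sub-maximal endpoint into the treadmill protocol in 6.1.3. Section 5.7 would still need to name the treadmill test.

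The first route costs about one sentence in each of three sections, plus the form if needed. Its downside is that a few women may contribute walk-based estimates of VO2max in place of treadmill measurements. That touches a secondary measure only. Using the same test at baseline and week 12 for each woman would keep her change score within one method.
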